In addition to the more common manifestations of LAL Deficiency, other clinical presentations and complications have been described, including pulmonary hypertension (Cagle et al., 1986), severe hypersplenism and splenic infarcts (Guzzetta et al., 1990), and mesenteric lipodystrophy (vom Dahl et al., 1999). Growth failure, defined as > 2 standard deviations below normal weight and height measurements for age, has been noted in some children and adults with LAL Deficiency. Gastrointestinal involvement occurs in most LAL Deficiency subjects. However, infants with LAL Deficiency typically present with chronic diarrhea, emesis, malabsorption and failure to thrive.

LAL Deficiency presenting in infants, historically called Wolman disease, is a more rare presentation of the disease and is usually fatal within the first 6 months of life. Named after the physician who first described it (Abramov et al., 1956), this is the most aggressive presentation of LAL Deficiency, with growth failure as the predominant clinical feature and a key contributor to the early mortality. Rapidly progressive hepatic disease, as evidenced by liver enlargement, elevation of transaminases, hyperbilirubinemia, coagulopathy, and hypoalbuminemia, also occurs in these infants and contributes to mortality (Anderson et al., 1999; Mayatepek et al., 1999).

At present, there are no therapies approved by regulatory authorities for the treatment of LAL Deficiency. In infants, a variety of supportive therapies are used in an attempt to mitigate some of the effects of this rapidly fatal disease. Although some temporary stabilization of the clinical condition has been described, these interventions are not believed to substantially modify the outcome in affected subjects (Hoeg et al., 1984; Meyers et al., 1985). With few exceptions, success has not been achieved using bone marrow/hematopoietic stem cell transplantation. These methods are frequently limited in use and/or associated with high mortality due to the condition of the subjects at the time of diagnosis. Additionally, bone marrow/hematopoietic stem cell transplantation carries the inherent risks associated with these procedures, including graft-versus-host disease (Krivit et al., 2000; Stein et al., 2007; Tolar et al., 2009; Yanir et al., 2013).

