2.2. Secondary Objectives

The secondary objectives of this study are:

- To evaluate effects of sebelipase alfa relative to Baseline assessment of lipid metabolism and liver abnormalities (including histopathology);
- To evaluate the effects of sebelipase alfa on additional clinical parameters of LAL Deficiency including those not previously well characterized in the literature;
- To evaluate the effects of sebelipase alfa on growth parameters in pediatric subjects presenting with evidence of growth delay;
- To evaluate the immunogenicity of sebelipase alfa.

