3.2.1.2. Efficacy

Literature review and insights from completed and ongoing clinical studies and the nonclinical disease model (see [Section 1.3](#)) suggest that a successful therapy for LAL Deficiency should mitigate the liver abnormalities and correct the dyslipidemia associated with the disease. Therefore, the study will investigate changes or percent changes over time from Baseline including the following:

- Decrease in ALT;
- Decrease in AST;
- Decrease in LDL-C;
- Decrease in non-HDL-C;
- Decrease in TG;
- Increase in HDL-C;
- Decrease in Child-Pugh status for subjects with Child-Pugh class C or B at Baseline;
- Decreased United Kingdom Model for End-Stage Liver Disease (UK-ELD) score;
- Improvement in liver histopathology;
- Decrease in liver and spleen volume by magnetic resonance imaging (MRI);
- Decrease in liver fat fraction by MRI.

Growth failure and other manifestations of impaired growth occur in subjects with LAL Deficiency. Early growth failure is the predominant clinical feature of LAL Deficiency in infants, and a key contributor to the early mortality. Positive effects on growth in subjects with LAL Deficiency would be supportive of a favorable effect of sebelipase alfa. Therefore, for pediatric subjects with evidence of impaired growth at Baseline, efficacy endpoints will also include changes over time in the following growth parameters:

- For subjects ≤ 24 months of age, z-scores and percentile scores based on World Health Organization (WHO) growth charts ([WHO Multicentre Growth Reference Study Group, 2006](#) and [2007](#)) will be determined for the following parameters:
 - Weight-for-age (WFA);
 - Weight-for-length;
 - Length-for-age;
 - Body-mass-index (BMI)-for-age;
 - Head circumference-for-age.

- For subjects > 24 months of age to 18 years, z-scores and percentile scores based on Centers for Disease Control and Prevention (CDC) growth charts ([Kuczmarski et al., 2002](#)) will be determined for the following parameters:
 - WFA;
 - Weight-for-stature (weight-for-height);
 - Stature-for-age (SFA);
 - BMI-for-age.
- For all subjects < 18 years, the proportion of subjects who meet criteria for under nutrition (underweight, wasting, and stunting) based on WFA, weight-for-length/weight-for-stature, and length-for-age/SFA, respectively ([UNICEF, 2009](#)), and combinations of these indicators, will be determined.

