6.1.1. Dose Escalation Criteria

Dose escalation up to $3 \text{ mg}\cdot\text{kg}^{-1}$ qw will be considered for each individual subject based on observed safety and tolerability and disease progression. Dose escalation will occur at the discretion of the Investigator and with approval of the Sponsor. An initial dose increase to $3 \text{ mg}\cdot\text{kg}^{-1}$ qow may be considered if the subject meets dose escalation criteria (as defined below), after receiving at least 8 consecutive infusions at the initial dose. A further increase in dose to $3 \text{ mg}\cdot\text{kg}^{-1}$ qw may be considered if a subject continues to demonstrate persistence of disease manifestations after receiving at least 8 consecutive infusions at a dose of $3 \text{ mg}\cdot\text{kg}^{-1}$ qow.

Prior to considering a dose increase, the subject will be evaluated for other potential causes of any observed clinical manifestations (e.g., initiation of a potentially hepatotoxic concomitant medication in a subject with abnormal ALT or AST, missed study infusions, or development of viral or autoimmune hepatitis or other alternative etiology of liver disease or inadequate weight gain). Protocol defined clinical laboratory assessments will be modified around any dose modification, as described in [Section 5.9](#).

A subject **meets dose escalation criteria** when any of the following are present:

- ALT or AST remaining abnormal, and either not improved or worsened from Baseline after 8 consecutive infusions from Baseline or worsened from the previously achieved lowest value over the preceding 8 consecutive qow infusions;
- LDL-C or triglyceride remaining abnormal, and either not improved or worsened over the preceding 8 consecutive qow infusions;
- The subject is < 18 years of age at the time of assessment for dose escalation, has a WFA z-score that is 2 standard deviations below the mean that either did not improve or worsened during the preceding 6 months, and the subject did not miss more than 20% of study infusions during the preceding 6 months. All possible etiologies for inadequate weight gain, not related to LAL Deficiency, will be ruled out by the Investigator before considering a dose increase.

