8.8.3. Anthropometric Parameters

Anthropometric indicators of growth status (WFA, plus additional parameters if sufficient data are available) will be evaluated for subjects < 18 years of age. Weight-for-length/weight-for-stature and BMI, if computed, will be derived from data on weight and length/stature. Anthropometric parameters will be plotted on standard growth curves. Z-scores and percentiles based on the age-gender standardized norms will be calculated in accordance with the methodology described by the WHO (subjects \leq 24 months) or CDC (subjects > 24 months to 18 years) and using the growth charts relevant to the respective methodology. When possible, historical data on growth parameters will also be incorporated into the analyses. The primary means for describing effects of sebelipase alfa on anthropometric parameters will be graphical displays; tables may be generated in support of the graphs. In addition, the percentages of subjects who meet criteria for under nutrition (underweight, stunting, and wasting) will be tabulated at each time point.

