Following a screening period of up to 45 days, each eligible subject will receive an intravenous (IV) infusion of SBC-102 at an initial dose of 1 mg/kg every other week (qow). A dose escalation to 3 mg/kg qow - and subsequently to 3 mg/kg every week (qw) - may be considered for a subject who satisfies the criteria outlined in Section 6.1 of the study protocol. Each subject will receive up to 96 weeks of treatment, then proceed to an expanded treatment period for a maximum of 48 weeks, after which a follow-up phone call will be conducted to assess adverse events (AEs) and concomitant medications approximately 30 days later.

The primary objective of the study is to evaluate the safety and tolerability of SBC-102 in LAL-D subjects who have not been previously studied.

The secondary objectives are:

- to evaluate effects of SBC-102 relative to Baseline assessment of lipid metabolism and liver abnormalities (including histopathology);
- to evaluate the effects of SBC-102 on additional clinical parameters of LAL-D including those not previously well characterized in the literature;
- to evaluate the effects of SBC-102 on growth parameters in pediatric subjects presenting with evidence of growth delay;
- and to evaluate the immunogenicity of SBC-102.

[figure not shown]
The exploratory objectives are:

- to further characterize the pharmacokinetics (PK) of SBC-102 in pediatric subjects, subjects with severe hepatic dysfunction, and those who have had a previous liver or hematopoietic stem cell transplant;
- and to evaluate the effect of SBC-102 on health-related quality of life (HRQOL) assessments.

An independent program-level safety committee (SC) appointed by the Sponsor will provide additional oversight of subject safety in this study through periodic and ad-hoc reviews of safety data.

A schematic of the study is provided in Figure 1. Further details on target population, inclusion/exclusion criteria, schedule of assessments and study procedures are available in the study protocol.

Figure 1: Study Flow Diagram

^a Each subject will initiate treatment in the open-label extension period (Week 100) at the same dose of sebelipase alpha they received during the last infusion of the treatment period (Week 96), unless criteria for dose modification are met (see Section 6.1 of Study Protocol).

^b Refer to Section 6.1 of Study Protocol for dose escalation criteria.

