4.1. Changes from Analyses Specified in the Protocol

The following items are specified in the protocol and are not part of this analysis plan:

- The urinalysis summary of the change from baseline will not be summarized. However urinalysis results will be provided in the subject listings.
- The summary of the change in vital signs during and after infusion relative to pre-infusion values will not be summarized; instead, the change from baseline (defined below) to each post-baseline visit will be summarized. Given that multiple vital sign measurements are taken at each post-baseline visit, the average of the measurements within a visit will be summarized.
- At the time of this Statistical Analysis Plan (SAP) amendment, only 2 subjects have been anti-drug antibody (ADA) positive. As a result, a clarification was added that many of the ADA analyses will only be performed in the event that at least 5 subjects are ADA positive.
- The effect of sebelipase alpha on growth parameters in pediatric subjects will be evaluated among all subjects younger than 18 years old. The protocol specifies analyzing these data conditional on subjects having had manifestations of impaired growth. However, the analysis will not be limited to subjects showing signs of impaired growth.
- The AE table showing the incidence of AEs across time intervals will not be presented.
- The protocol indicates that percentages will be calculated including subjects with missing values.
 However, percentages will be based on subjects with non-missing values unless otherwise specified.

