- In the appendices, the scoring of the Functional Assessment of Chronic Illness Therapy (FACIT)-Fatigue was changed to correctly reflect that Items 7 and 8 are not reverse scored, and that the Pediatric Quality of Life Inventory (PedsQL) Total Score and Psychosocial Health Summary Score are not computed if at least 1 scale score is missing.

The following summaries have been removed from this version of the SAP:

- Spaghetti plots of laboratory parameters are replaced with waterfall plots of the percent change from baseline to Week 96. Spaghetti plots may be provided.
- For anthropometric measures in which results are compared to population norms using z-scores and percentiles, only the percentiles will be summarized.

5. **DEFINITIONS**

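### No committed SAP table estimates how much growth changed in the growth-delayed children named in the secondary objective; the only continuous growth summary is the percentile, and it is not split by growth delay

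*SAP*

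**What the plan says.** **Objective and endpoint.** Protocol 2.2 sets the objective: "To evaluate the effects of sebelipase alfa on growth parameters in pediatric subjects presenting with evidence of growth delay". SAP section 4 repeats it. Protocol 3.2.1.2 makes it an endpoint: "for pediatric subjects with evidence of impaired growth at Baseline, efficacy endpoints will also include changes over time in the following growth parameters". It then lists z-scores and percentiles on WHO charts (up to 24 months) and CDC charts (older).

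**Population.** SAP 4.1 widens the growth analysis to everyone younger than 18: "However, the analysis will not be limited to subjects showing signs of impaired growth".

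**Summary measure.** SAP 4.2 says: "For anthropometric measures in which results are compared to population norms using z-scores and percentiles, only the percentiles will be summarized". SAP 5.2.1 still lists z-scores as endpoints and 7.3.4 still calculates them. The general rule in SAP 7.3 gives continuous endpoints observed value, change and percent change, with 95% confidence intervals. Section 7.3.4 does not repeat that rule for growth.

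**Subgroups.** SAP 7.12 splits efficacy outcomes by age (under 12, 12 and over), gender, lipid-lowering use, mutation category, fibrosis or cirrhosis status and ALT, and also summarizes ages 2-4. Growth delay is not on the list. SAP 6, 7.3 and 7.13 allow other subgroups but commit to none.

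**Other growth displays.** SAP 7.3.4 keeps one growth curve per subject and the percentages underweight, stunted and wasted at each time point. SAP 7 puts all collected data in listings. In Protocol 8.8.3 the "primary means for describing effects of sebelipase alfa on anthropometric parameters will be graphical displays; tables may be generated in support of the graphs".

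**The concern.** The objective asks what happened to growth in delayed children, and the planned tables do not isolate them. A reader who wants to know how much that group gained would find a percentile summary that mixes them with children of normal growth, counts of threshold crossings, and individual curves to read by eye.

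The chosen scale adds to this. Equal gains in SD units give very unequal gains in percentile points, and the smallest numbers fall to the children furthest below normal. A real gain in a severely delayed child could therefore look negligible in the only continuous growth table.

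**Working it through.** **1. The SAP's own figure.** SAP 9.4.11.4 converts z to percentile with the standard normal distribution: percentile = 100 × Φ(z). It gives 97.7 for z = +2. Check: 100 × Φ(2) = 97.72, with 2.28 above it. The figure reproduces.

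**2. A 1-SD gain on the percentile scale.** Change = 100 × [Φ(z+1) − Φ(z)]. Percent change = that change divided by 100 × Φ(z), times 100.

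| Start z | Percentile before | After | Change (points) | Percent change |
|---|---|---|---|---|
| -3.5 | 0.023 | 0.621 | 0.6 | +2569% |
| -3 | 0.135 | 2.275 | 2.1 | +1585% |
| -2.5 | 0.621 | 6.681 | 6.1 | +976% |
| -2 | 2.275 | 15.866 | 13.6 | +597% |
| -1.645 (5th percentile) | 5.00 | 25.95 | 21.0 | +419% |
| -0.5 | 30.85 | 69.15 | 38.3 | +124% |

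The same gain is 38.3 / 2.14 ≈ 18 times larger in points from z -0.5 than from z -3. Percent change, if the SAP 7.3 rule is applied to percentiles, reverses the order. On the z scale every row is 1.00.

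**3. Do the undernutrition counts fill the gap?** SAP 9.4.11.3 puts cut-offs at -2 SD, and at -3 SD for severe underweight.

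- Gains can stay inside a band. Height-for-age from -3.5 to -2.5 moves the percentile 0.6 points and leaves the child counted as stunted. Weight-for-age from -2.9 to -2.1 moves it 1.79 − 0.19 = 1.6 points and leaves the underweight category unchanged.
- The counts usually show direction all the same. Assume 5 of 20 children delayed, each gaining 1 SD, with a fluctuation SD of 0.3 (200,000 simulated sets). The number below -2 SD falls in 95% of sets if the delayed children start at z -3, and in more than 99.9% if they start at -2.5.

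The counts therefore give direction but not size.

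**4. Which scale does the Protocol use?** Both.

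- Entry criteria 4c and 5d (Protocol 4.3) are percentile rules: below the 5th percentile for a stated time, or a fall across two major percentile lines.
- Protocol 1.1.2 works in SD units: "Growth failure, defined as > 2 standard deviations below normal weight and height measurements for age". The growth criterion in Protocol 6.1.1, cited here only for its scale, asks whether a child "has a WFA z-score that is 2 standard deviations below the mean that either did not improve or worsened during the preceding 6 months".

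**5. Regression to the mean in an impaired-growth table.** Children picked for low values tend to drift up without any effect of treatment. Assume unit variance and equal correlation r between visits.

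- One value below the 5th percentile, patients following the N(0,1) reference: the mean z of those selected is -2.063, so the apparent gain is (1 − r) × 2.063, or 0.10, 0.21 and 0.41 SD for r = 0.95, 0.90 and 0.80.
- Two values below it (simulated): about 0.06, 0.11 and 0.24 SD. If the patient mean is z -1 instead, about 0.03, 0.07 and 0.15 SD.

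**6. Change of growth reference.** Entry is above 8 months and the treatment period runs to 96 weeks: 96 × 7 / 30.4 ≈ 22 months, and 8 + 22 = 30 months. Every child who starts on the WHO charts and completes Week 96 has moved to the CDC charts. This affects change in z-score and change in percentile alike.

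**The case against.** **The mismatch is partly inherited, and it is disclosed.** Protocol 8.8.3 already evaluates growth in all subjects under 18, with graphs first and tables optional. SAP 4.1 declares the wider population openly. A reader might infer that the SAP dropped a table the Protocol had promised. The documents do not support that, because no such table was promised. The gap against the objective and against Protocol 3.2.1.2 still stands.

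**The percentile summary is not a single pooled figure.** A reader might infer that all subjects under 18 are lumped together. SAP 7.12 splits efficacy outcomes by age, gender and other factors where each subgroup has at least 5 subjects. None of those splits is by growth delay.

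**The data stay visible.** With few children, a curve for each plus listings lets a reader follow every delayed child. That is true, and it limits the harm. It does not give a group estimate.

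**Other subgroups are allowed.** They are, but only as an option or post hoc.

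**Percentiles are a legitimate scale here.** A reader might infer that the Protocol judges growth only in z-scores. It does not: its entry rules are percentile rules. Preferring z for the summary is good practice rather than a requirement of the documents.

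**The severe distortion is shown only at assumed baselines.** This stands. At the one documented cut, the 5th percentile, a 1-SD gain shows as 21.0 points, which nobody would miss.

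**Conclusion.** The point holds in a limited form. The secondary objective and Protocol 3.2.1.2 name children with growth delay or impaired growth at Baseline, and no committed table estimates the size of the change in them. The only continuous growth summary is on a scale that compresses gains at very low z: 0.6 points per SD from z -3.5 and 2.1 from z -3, against 38.3 from z -0.5.

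The percentile figures follow exactly from the SAP's conversion. How much they matter depends on how many children are delayed and how far below normal they start, and the documents give neither. No dilution figure for the combined table can therefore be claimed. The percent-change figures apply only if the general rule in SAP 7.3 is carried over to percentiles. The regression-to-the-mean figures illustrate assumed correlations and patient means; they are not expected ranges.

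A reader might conclude that growth effects in these children will go unseen, or that the study is undermined. Neither follows, since the curves, listings and undernutrition percentages remain. This is a reporting gap in a descriptive secondary objective. Severity: COULD.

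**What to change.** Amend SAP 7.3.4 and align 4.1, 4.2 and 7.12:

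1. Tabulate observed z-score and absolute change in z-score beside the percentiles. Give no percent change for either.
2. Present this for all subjects under 18 and for those with impaired growth at Baseline. Define the latter by the anthropometric parts of inclusion criteria 4c and 5d, with their durations, whatever the route of entry. Where growth history is missing, use Baseline below the 5th percentile and flag those children.
3. If fewer than 5 children qualify, list each child's Baseline z and changes in z instead of dropping the table under the 5-per-subgroup rule.
4. For children who pass 24 months on study, flag the WHO-to-CDC change and either show the change on a single reference as a check or report them separately, so that a change of chart is not read as growth.
5. State beside the table that the subset is uncontrolled and that regression to the mean may contribute to any apparent gain.

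**Cost.** SAP wording and one extra set of small descriptive tables. The z-scores are already derived for the percentiles and the undernutrition cut-offs. The duration and percentile-crossing rules need historical growth data, which SAP 7.3.4 already plans to use where possible. The single-reference check needs one further derivation for the youngest children.

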5.1. Safety

5.1.1. Primary Endpoint(s)

This study is designed primarily to evaluate the safety of IV infusion of SBC-102. Safety will be assessed based on: incidence and severity of TEAEs, serious adverse events (SAEs), and IARs; changes from baseline through trial completion in vital signs, Electrocardiogram (ECG), and routine clinical laboratory tests (chemistry, hematology, urinalysis); physical examination findings; use of concomitant medications/treatments; functional and overall development measured using the Denver II Development Screening Test; and incidence/titer of antibodies to SBC-102.

5.1.1.1. Adverse Events (AEs), Serious Adverse Events (SAEs) and Infusion-Associated Reactions (IARs)

See Section 7.1 of study protocol for definitions.

